## 1.0 Objectives

### 1.1 Study Objectives

The specific objective of this proposal is to utilize the practice of telemedicine via connected health devices to enable the guided performance of a remote pulmonary function test (rPFT) in the home. The rationale for this study is to determine whether telemonitoring of respiratory health can help exceed standards of ALS care.

#### Part 1: Demonstrate the reliability of remote pulmonary function testing, performed via telemedicine, for monitoring respiratory function in patients with amyotrophic lateral sclerosis (ALS)

*Primary Hypothesis:* There is no difference in the results of PFT and rPFT for respiratory assessment of FVC and MIP.

*Secondary Hypothesis:* The respiratory therapist, patient, and caregiver will express confidence in conducting the rPFT, as determined by surveys of procedure acceptance.

#### Part 2: Monitor more closely the course of respiratory function over time in patients with ALS by using remote pulmonary function testing, performed via telemedicine.

*Primary Hypothesis:* Home respiratory assessment enables thresholds for Non-invasive ventilation (NIV) recommendation to be met in the experimental group significantly closer to the initiation criteria, at a time when quality of life is higher, compared to the control group.

*Secondary Hypothesis:* Telemonitoring of respiratory health in the experimental group will maintain higher quality of life, and lengthen survival.

### 1.2 Primary Study Endpoints

Part 1: The primary endpoint is completion of a standard PFT and an experimental rPFT during a single clinic appointment. At the endpoint, study outcomes will include:

- 1) The best FVC and MIP results from that visit's PFT
- 2) The best FVC and MIP results from that visit's rPFT
- 3) Survey responses from study participants.

Part 2: The primary endpoint for each person in the study is the completion of the fifth clinical visit, during which the control arm should have complete data for the following outcomes:

- 1) The results of five PFT administrations at 3 month intervals
- 2) Patient and caregiver monthly surveys

In addition, the experimental group will have engaged in eight additional guided rPFT assessments with the respiratory therapist over the telemedicine interface.

### 1.3 Secondary Study Endpoints

Study participants will be followed after completion of study procedures, and their survival data will be recorded.

## 2.0 Background

### 2.1 Scientific Background and Gaps

#### Non-invasive ventilation (NIV) lengthens survival and improves QoL for patients with ALS.

According to the Quality Measurement Set put forth by the American Academy of Neurology (AAN), two parameters of high importance in ALS care are monitoring of respiratory function and management with NIV [Miller2013]. The practice parameter of the AAN regarding ALS care states that NIV is effective in prolonging survival and slowing the rate of respiratory decline [Miller2009]. NIV has been documented to have a positive effect on QoL in the areas of sleep quality, daytime sleepiness, physical fatigue, and

depression [Butz2003]. NIV is recommended when a patient presents with either an FVC≤50% predicted or a MIP > -60 cm H2O [Miller2009]. It is recommended that PFTs be done at least once every three months, and that doctors discuss options for NIV support regularly.

The multidisciplinary clinical model may not provide optimal management for patients with rapidly progressing respiratory symptoms.

Although disease course varies substantially, some patients experience rapid respiratory decline. In prospective study of 38 newly diagnosed patients, half presented with chronic hypoventilation after one year, necessitating the introduction of NIV [LoCoco2006]. The authors suggest that efforts should be made to evaluate pulmonary function in these patients at least once every month. Furthermore, it has been shown that early initiation of NIV at an FVC threshold of 65% predicted was associated with a significant increase in the median time from ALS diagnosis to death [Lechtzin2007]. The current practice of quarterly respiratory assessment may leave some individuals in danger of developing to untreated respiratory insufficiency or beginning treatment later than would be optimal or other more scientific wording.

Telemedicine has impacted other areas of neurology, but is understudied for efficacy in ALS.

The practice of telemedicine involves the delivery of medical care via long-distance and electronic communication between a health care professional and a patient or another health care professional. This type of intervention can expand medical coverage into underserved regions, while maintaining the high quality of care. Success with telemedicine in other areas of neurology, such as in the treatment of Parkinson's disease [Samii2006], epilepsy [Ahmed2008], and stroke [Demaerschalk2009], provide a framework for achieving positive outcomes.

It is largely unknown whether remotely-provided multidisciplinary care results in outcomes for ALS patients and their caregivers that are comparable to those achieved with traditional care. A review by Hobson et al. identified 32 publications addressing telemedicine in ALS [Hobson2016], which concluded that patients are comfortable using the videoconferencing interface to discuss most concerns, they appreciated the reduced travel time and costs, and the use of telemedicine extended the period for which they received multidisciplinary care. Some programs offered live interaction with providers as a way to delivered care to individuals in rural areas with no alternative treatment options [ALS-Maine2010, Bedlack2014]. Other models utilized a traveling nurse to perform the assessment in the patient's home, which is stored and forwarded to the appropriate providers at the multidisciplinary clinic [Pulley2015, McClellan2013]. Others have taken on a more passive role, with monitoring of oximetry and non-invasive ventilation (NIV) data by a nurse led to fewer hospital visits, and higher treatment adherence [Pinto2010, Vitacca2010, Ashcroft2016].

Despite these results, Hobson concludes "*There is limited evidence to recommend the use of telemedicine or telehealth in the case of patients with ALS. Using telehealth as an alternative to clinic visits appears technically feasible but further research needs to establish its safety and effectiveness*" [Hobson2016]. To address gaps in telemedicine care, randomized controlled clinical trials must be used to identify methods that can meet or surpass the standards of in-person assessment.

## 2.2 Previous Data

Preliminary work by our group as part of a pilot study assessing the benefits of ALS telemedicine has shown that the practice of live telemedicine is viewed favorably by ALS patients, caregivers, and multidisciplinary ALS team members, although less so by the latter group (Figure 1, [Morris2016, Geronimo2017]). Overall, the three rater groups were concerned that the lack of physical contact lessened the ability for providers to deliver equal care. This led us to identify and act upon one area of care that could be improved in telemedicine – assessment of breathing function.

[figure not shown]

Figure 1: Patient (P), caregiver (C), and health care provider (H) ratings of the ALS telemedicine pilot in four domains [Geronimo2017]. Circles containing an X mark the medians, thick lines span the first to third quartile of data, with thin lines extending up to two times this range. Outliers are those small circles outside this range

### 2.3 Study Rationale

The rationale for this study is to determine whether telemonitoring of respiratory health can help exceed standards of ALS care.

## 3.0 Inclusion and Exclusion Criteria

### 3.1 Inclusion Criteria

#### Part 1

Patients:

- 1) Possess a diagnosis of definite, probable, probable laboratory-supported, or possible ALS by revised El Escorial research criteria [Brooks2000], or a diagnosis of primary lateral sclerosis (PLS, upper motor neuron involvement only) or progressive muscular atrophy (PMA, lower motor neuron involvement only).
- 2) Be 18 years of age or older.
- 3) Have a caregiver available to participate in the study

Caregivers:

- 1) Be 18 years of age or older, of either gender.
- 2) Be able and willing to provide informed consent.

Controls:

- 1) Be 18 years of age or older, of either gender.
- 2) Be able and willing to provide informed consent.

Respiratory Therapist

- 1) Be a member of the Hershey Medical Center ALS multidisciplinary care team.
- 2) Be able and willing to provide verbal informed consent after receiving a summary explanation of research (SER).

#### Part 2:

Patients:

- 1) Possess a diagnosis of definite, probable, probable laboratory-supported, or possible ALS by revised El Escorial research criteria.
- 2) Be 18 years of age or older.
- 3) Have a caregiver available to participate in the study.

- 4) Symptom onset within the last three years.
- 5) Intent to attend the Penn State Hershey ALS clinic every three months for the next year.
- 6) Have home wireless internet service sufficient for engaging in telemedicine sessions.

### **3.2 Exclusion Criteria**

#### Part 1

Patients:

- 1) Cognitive impairment, as judged by the ALS clinic neurologist, that prevents participation in the study.
- 2) ALS Functional Rating Scale (ALSFRS-R) [Cedarbaum1999] score on day of screening of less than or equal to 2 on all of the items for speech, swallowing, and salivation. These items are indicators of bulbar dysfunction, which limits the reliability of PFT administration.

Caregivers: None

Controls: None

Respiratory Therapists: None

Part 2 imposes additional exclusion criteria for patients only.

Patients:

- 3) Use of NIV or diaphragm pacer at time of obtaining informed consent.
- 4) FVC  $\leq$ 50% predicted or MIP  $>$  -60 cm H2O.

### **3.3 Early Withdrawal of Subjects**

#### **3.3.1 Criteria for removal from study**

Participants may voluntarily withdraw from the study at any time. The research team may also terminate the study if the participant team exhibits one or more of the exclusion criteria during the course of the study.

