Following the initial visit (month 0), participants will undergo randomization. Those randomized to the experimental group will be shipped an rPFT kit and scheduled for monthly telemedicine appointments between clinic visits. On the dates of the telemedicine appointments, the respiratory therapist administers the study survey and conducts an rPFT from clinic with the patient in their home. This is repeated for the 2nd month. On the 3rd month, the participant dyad is seen by the therapist during their normal clinic visit. This pattern is repeated until the 5th clinical appointment (including the visit at month 0), resulting in 5 in-person assessments and 8 intermediate tele-assessments over the course of approximately 12 months. The control arm will receive standard assessments during regular ALS clinic appointments (Table 1), and be required to complete a study survey each month. Study procedures will be followed until the study endpoint at month 12, even if NIV is initiated during this period. The treating neurologist will make the decision to end the protocol early if the patient is unable to perform the procedures. The patient can also opt to end the study at any time.

The study survey is administered once a month for participants in both study arms and consists of four parts. The initial survey administered at month 0 will be completed with a researcher present. The remaining surveys will be completed online. If it coincides with administration of a PFT or rPFT, it will be administered first. It is designed to measure the impact of daytime breathlessness and sleepiness on QoL and consists of the following components.

- 1) Sleep Apnea Quality of Life Index (SAQLI) - part D [Flemons1998]. It is designed to assess quality of life pertaining to sleep disturbances, as well as the impact of treatment on QoL. It has been used as a sensitive measure of health-related QoL in ALS [Bourke2006, Jackson2001, Bourke2003].
- 2) Motor Neurone Disease Dsypnoea Rating Scale (MDRS) - subscale D [Dorman2007]. Dorman et al. described an ALS-specific assessment, the Motor Neurone Disease Dsypnoea Rating Scale (MDRS), as one with high construct validity and responsiveness. The dyspnea subscale (MDRS-D) of this tool has patients choose which activities of daily living they have experienced shortness of breath in the past two weeks and how severe the episode was [Dougan2000].

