- 3) Short Form 36 (SF-36) [Ware1992]. This is a generic, coherent, and easily administered quality-of-life measures which has been shown to be sensitive for mental and physical health assessment in ALS [Bourke2006, Jackson2001, Bourke2003].
- 4) SAQLI parts E and F (NIV users only). These sections ask about problems that may have arisen due to NIV use and how respiratory symptoms may have been alleviated due to treatment during this period.

Each session concludes with recommendations from the therapist based on the results of respiratory tests. These can include behavioral modifications or recommendation for NIV. Recommendation of NIV is based on a measured FVC  $\leq$ 50% predicted or for dyspnea accompanied by MIP  $>$  -60 cm H2O. This recommendation will be reviewed by the ALS clinic neurologist. If the decision is made to initiate NIV, the ALS clinic physician will provide an order, and the ALS clinic nurse will arrange for initiation of in-home NIV via a third-party vendor according to usual standards of care.

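### Part 2 withdrawal rules: 3.3.1 allows removal at the FVC threshold the trial waits for, against 7.2.2, and 3.3.2 ends follow-up of withdrawn randomised patients

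*Combined protocol and SAP*

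**What the plan says.** **Removal.** Section 3.3.1 states that study staff "may also terminate the study if the participant team exhibits one or more of the exclusion criteria during the course of the study". Section 3.2 lists two patient criteria under Part 1, then adds: "Part 2 imposes additional exclusion criteria for patients only". The four criteria differ in timing:

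- Criterion 1 is "Cognitive impairment, as judged by the ALS clinic neurologist, that prevents participation in the study". It has no time anchor.
- Criterion 2 (bulbar ALSFRS-R items) is fixed to the day of screening.
- Criterion 3 (NIV or diaphragm pacer) is fixed to the time of consent.
- Criterion 4 (FVC at or below 50% predicted, or MIP above -60 cm H2O) has no time anchor.

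**Continuation.** Section 7.2.2 says: "Study procedures will be followed until the study endpoint at month 12, even if NIV is initiated during this period". On early stopping it says: "The treating neurologist will make the decision to end the protocol early if the patient is unable to perform the procedures". It adds that the patient may opt out at any time.

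**Trigger.** Under 7.2.2, NIV is recommended for FVC at or below 50% "predicted or for dyspnea accompanied by MIP" above -60 cm H2O. The survey is timed relative to the breathing test: "If it coincides with administration of a PFT or rPFT, it will be administered first".

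**After withdrawal.** Section 3.3.2 has staff collect the equipment from the home and offers an optional endpoint assessment to record the reason for leaving. It then rules out follow-up and permits replacement from the waitlist. Section 1.3 plans survival recording after study procedures are completed. Sections 1.1 and 7.1 make one-year quality of life and survival between-arm comparisons in Part 2.

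**The concern.** Two staff members could handle the same patient differently. One who follows 3.3.1 may end participation when FVC falls to 50%. One who follows 7.2.2 keeps testing and surveying to month 12. Any removal under criterion 4 would depend on respiratory decline. It could also come sooner in the experimental arm, where monthly testing detects the crossing earlier. Such a patient would miss the fifth visit that defines the Part 2 endpoint in 1.2.

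The follow-up rule is a separate problem and does not need anyone to be removed under criterion 4. A randomised patient who leaves for any reason contributes no further quality-of-life data under 3.3.2, and apparently no survival data. Leaving a year-long ALS study may well go with decline, so the missing outcomes are unlikely to be a random subset. Section 8.3 does not say who is analysed or how withdrawals are handled.

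**Working it through.** **1. Do 3.3.1 and 7.2.2 conflict?** The wording of 3.3.1 applies exclusion criteria after enrolment. Criteria 2 and 3 cannot newly arise, because each is fixed to a date at entry. Criterion 1 can arise later and is a sensible reason to stop. Criterion 4 can arise later, and its FVC limb is the event on which the Part 2 primary comparison (8.3) is built. Section 7.2.2 refers to NIV initiation rather than to criterion 4, but initiation follows from a recommendation based on the same FVC threshold. Reaching that threshold is neither inability to perform the procedures nor patient choice.

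**2. Which data are exposed?**

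- *FVC limb.* The survey precedes the test, so quality of life and FVC are both in hand at the triggering visit. The primary values survive. Later surveys, the fifth visit and survival do not, if the patient is removed and 3.3.2 then applies.
- *MIP limb.* Criterion 4 needs no dyspnea; the trigger in 7.2.2 does. (The background in 2.1 states no dyspnea condition.) A patient with MIP above -60 and no dyspnea could be removed before any recommendation, and the primary value would be lost. The documents give no basis for counting such patients.

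**3. How many patients reach the threshold?** Section 8.2 expects 75% to meet the NIV criteria: 0.75 × 40 = 30. Its simulation gives 80.6%: 0.806 × 40 = 32.2. These are patients to whom the clause could apply, not predicted removals.

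**4. Ceiling on lost surveys.** The 8.2 simulation was rebuilt with monthly FVC loss drawn each month from normal(3.5, 3.4), no reading error, and trigger FVC at or below 50%. Tests fell at months 1 to 12 (experimental) or 3, 6, 9 and 12 (control), with 400,000 simulated patients per arm. Starting FVC is not given in the documents, so two assumed starts were used.

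| | Protocol 8.2 | Start 82% | Start uniform 50–100% |
|---|---|---|---|
| Reach threshold by month 12 | 80.6% | 81.0% | 81.0% |
| Mean FVC at trigger, exp. vs control | 47.0 vs 43.4 | 47.0 vs 43.5 | 47.0 vs 43.1 |
| Effect size | 0.964 | 0.94 | 1.00 |
| Reach before month 12, exp. vs control | – | 73.3% vs 48.2% | 76.0% vs 63.0% |
| Patients of 40 | – | 14.7 + 9.6 = 24.3 | 15.2 + 12.6 = 27.8 |
| Surveys after the trigger month, exp. | – | 50.6/240 = 21.1% | 93.5/240 = 38.9% |
| Surveys after the trigger month, control | – | 34.5/240 = 14.4% | 75.9/240 = 31.6% |
| Gap between arms | – | 6.7 points | 7.3 points |

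Here 240 = 20 patients × 12 post-baseline months, ignoring deaths and missed surveys. Both starts come close to the protocol's outputs, so the documents do not identify the level. The loss rows assume that every patient is removed on the trigger date.

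**5. Does 3.3.2 reach randomised patients?** Yes. It collects equipment from homes, and 7.2.2 says: "Those randomized to the experimental group will be shipped an rPFT kit". A kit in a Part 2 home therefore means a randomised patient, and the text of 3.3.2 is not limited by arm. No withdrawal rate is given, so only the loss per patient can be stated. One patient who leaves just after month 6 forgoes 6 of the arm's 240 surveys (6/240 = 2.5%), and that patient's later survival, 1 of 20 (5%), is not recorded.

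**The case against.** The best defence is that 3.3.1 is a general, optional clause covering both Parts, while 7.2.2 is the specific Part 2 rule. The whole design waits for FVC to reach 50%, so staff would naturally read criterion 4 as an entry criterion. Section 7.2.2 also does not say that its two reasons for stopping are exhaustive. Much of this stands: it is why the number removed may be none and why the first part is a clarification. It does not dispose of the point. No text gives 7.2.2 precedence, and 3.3.1 expressly applies the criteria after enrolment.

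It is also fair to say that the damage falls on secondary comparisons for which 8.3 names no test, and that 1.3 may have been meant to include withdrawn patients. But 1.3 speaks of completing procedures and 3.3.2 points the other way, so the text needs settling.

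A reader might infer that replacing randomised patients is itself a source of bias and should be banned. The documents do not support that. Bias would come from dropping withdrawn patients, and nothing says their data are discarded or that analysis departs from assigned arm. Adding randomised patients does no harm if the withdrawn ones stay in, and 0.75 × 20 = 15 per arm is exactly the planned number, with no margin for attrition.

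**Conclusion.** The point holds in two parts of unequal strength.

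- *Removal clause.* The conflict is real on the wording, but removal is discretionary and contrary to the specific Part 2 rule. The survey losses of 21% vs 14%, or 39% vs 32%, are hypothetical ceilings under an assumed starting FVC and universal removal; they are not forecasts. The gap of about 7 points between arms rests on the same assumption.
- *Follow-up rule.* This is the better supported part. Section 3.3.2 ends data collection for withdrawn randomised patients while 1.1 and 7.1 rely on one-year quality of life and survival by arm. Its size depends on a withdrawal rate that the documents do not give.

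A reader might go further and conclude that the clause strips the primary analysis of most of its patients. It does not. FVC-triggered values are collected before any removal, and the primary comparison covers only patients who reach NIV recommendation in any case. The one route to losing a primary value is MIP above -60 without dyspnea, and its frequency is unknown. Both parts should be corrected because the stated rules are wrong as written and cheap to change; no loss of primary data has been shown.

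**What to change.** - **3.2 and 3.3.1:** state that criterion 4 applies at enrolment only, and that reaching it or starting NIV is not a ground for removal from Part 2. Keep criterion 1 and inability to perform the procedures as reasons to stop procedures.
- **3.3.2:** replace the sentence ruling out follow-up with continued recording of survival, and of monthly surveys where the patient agrees, unless consent for this is withdrawn. Align 1.3 so that it covers withdrawn patients.
- **8.3:** analyse all randomised patients with available data by assigned arm.
- **Replacement:** extra patients may still be enrolled, but only as additional randomised patients, never in place of withdrawn patients' data.

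The cost is a short protocol amendment and a line of consent wording. Survival recording is already planned in 1.3, so the added work is limited to patients who withdraw.

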#### **3.3.2 Follow-up for withdrawn subjects**

The research team will follow up with withdrawn subjects at their home to collect the research equipment. If the participant team agrees, they will be given the endpoint assessment to document their reason for withdrawal. There will be no follow-up. The withdrawn subjects may be replaced by another patient and caregiver from the recruitment waitlist.

## **4.0 Recruitment Methods**

### **4.1 Identification of subjects**

Potential patient participants will be identified by study staff of the Penn State Hershey ALS center at the time they are seen for routine visits to the Penn State Hershey ALS Clinic, or based on their responses to recruitment letters (see below). Potential subjects may also learn of the study by a flyer posted in the ALS clinic area. Practice control participants will be recruited from clinical staff.

Respiratory therapists sought for participation in the study will be those providing respiratory therapy services to ALS patients in the clinic on the date of the study.

